Consent is discussed and agreed as per the separate consent form and participant information sheet from potential participants, in-line with the inclusion and exclusion criteria. Blinding is not employed as it is impractical and would obstruct study methods. The study will take place across at least one year to include the peak periods of seasonal pathogens.

Randomisation

Participants will be enrolled and assigned a participant identification number consecutively. Once a patient has been screened and consented a study team member will log onto the password-protected electronic randomisation website (sealedenvelope.com, which uses randomised permuted blocks) to obtain a randomisation code for the patient who will then be allocated to either the intervention or control group.

For those randomised to the interventional arm:

A stool sample will be taken by a member of research staff (doctor or nurse). In the event of the patient being unable to provide a timely stool sample, a rectal swab will be obtained with appropriate chaperone as per hospital policy. The sample is placed in Carey-Blair media and analysed on the FilmArray using the Gastrointestinal Panel, as per training delivered by the apparatus manufacturer. Test results are generated in about 1 hour. In the event of a run failure, the analysis run will be repeated using the same sample; if there is insufficient sample left, further samples may be taken if the participant consents. If a rectal swab was

tested initially, a stool sample will be subsequently obtained at the earliest opportunity and then tested and the results checked to ensure concordance.

The results of the test will be documented in the patient's case notes. In the event of a pathogen being detected, a member of the clinical team responsible for the patient will be directly informed. The participant will also be informed of the result. If a positive result for a bacterial pathogen is detected the clinical team will be directed to the local and national treatment guidelines for that pathogen.

For all positive and negative results the infection and prevention control team and the site managers responsible for side room allocation will be informed in real time.

Further laboratory stool testing will be at the discretion of the responsible clinical team.

For those randomised to the control group

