These patients will be managed according to standard clinical care. Laboratory stool testing will be at the discretion of the responsible clinical team and where performed will be by standard laboratory diagnostic testing.

A stool sample and/or rectal swab will also be taken from patients in the control group and stored for testing at a later date using the FilmArray GI panel. Samples will be taken on enrolment, frozen and stored, and run on the FilmArray at least 30 days after collection. The results will not influence patient care but is scientifically important as it will allow a direct comparison of diagnostic yield between the groups.

For both control and intervention groups:

Clinical and demographic data will be collected by the study team at the time of enrolment. After patients have been discharged or after 30 days (whichever is soonest), clinical data may be collected retrospectively from electronic and physical case notes, including electronic prescribing which will allow data relating to outcome measures to be recorded by the study team. These include: antibiotic use, duration of hospitalisation, isolation facility use, time to diagnoses and test turnaround time, in addition to safety outcomes and in line with all pre-specified outcome measures. All data will be entered onto a standardised case report form and entered into a secure database.

Participants may be approached for blood sampling (a maximum of 21mls) and additional stool samples and/or rectal swabs and/or vomitus samples to be stored for further study including immunological and pathogen sequencing. All samples left-over from testing may be used for further study. Participant consent for this is included in the consent form.

A participant experience and/or satisfaction survey may be collected from participants after their involvement in the trial.

6. Recruitment / screening / inclusion / exclusion criteria

Recruitment and Screening

Eligible patients in the acute medical unit (AMU), acute surgical unit (ASU) and emergency department (ED) and inpatient wards will be identified by research staff who will regularly review the comprehensive admissions IT systems daily.

Inclusion Criteria

- Aged 18 years or over.
- Has the capacity to give informed, written consent and is able and willing to adhere to the study procedures
- Is a patient in Southampton General Hospital ED, AMU, ASU or inpatient ward
- Can be recruited to the study

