 - within a 48 hour period of first triage by ED staff OR
 - within a 48 hour period of arrival on AMU or ASU or inpatient ward (if admitted directly to an inpatient ward)
- Has an acute diarrhoeal illness and /or vomiting*
- Has a duration of illness less of than or equal to 14 days

*An episode of acute diarrhoea is defined as the passage of at least 3 loose stools for at least 1 day.

Exclusion Criteria

- Patients not fulfilling inclusion criteria
- A palliative approach being taken by the treating clinicians
- Previously included in this study and re-presenting within the last 30 days after hospital discharge
- Declines to give stool sample and/or rectal swab

Involvement in other research trials is not necessarily an exclusion criterion. Concurrent, prior or subsequent enrolment in an observational study is not expected to be an exclusion criterion, except at the discretion of the PI.

7. Further information regarding the FilmArray Gastrointestinal

Panel

The FilmArray Gastrointestinal Panel is a rapid diagnostic test that uses nested RT-PCR followed by melt curve analysis to detect 22 targets. The apparatus takes about an hour to give results. It is deployable as a point-of-care test and the units will be housed in the acute areas for this study. The manufacturers are BioFire Diagnostics, [name] and their website is www.BioFireDx.com. BioFire Diagnostics is owned by bioMérieux. The FilmArray Gastrointestinal Panel is CE IVD marked and FDA (USA) approved.

The following targets are detectable:

Bacteria

Campylobacter (jejuni, coli and upsaliensis) Clostridium difficile (toxin A/B) Plesiomonas shigelloides Salmonella Yersinia enterocolitica Vibrio (parahaemolyticus, vulnificus and cholerae) Vibrio cholerae Diarrheagenic *E. coli/Shigella*: Enteroaggregative *E. coli* (EAEC) Enteropathogenic *E. coli* (EPEC) Enterotoxigenic *E. coli* (ETEC) *It/st* Shiga-like toxin-producing *E. coli* (STEC) *stx1/stx2 E. coli* 0157 Shigella/Enteroinvasive E. coli (EIEC)

Parasites

Cryptosporidium Cyclospora cayetanensis Entamoeba histolytica Giardia lamblia

Viruses

Adenovirus F 40/41 Astrovirus Norovirus GI/GII Rotavirus A Sapovirus (I, II, IV and V)

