The initial phase of this study was designed as an internal pilot study with exploratory outcomes and accurate samples size calculations were not possible. After recruiting 100 patients (50 per group) we now have accurate data on the mean and standard deviation of duration of side room use, and withdrawal rate, allowing us to calculate samples size needed for the primary outcome. 141 patients per group will give 90% power at a 0.05 significance level to detect a 1 day reduction in the mean duration of side room use; from 3 to 2 days (with a standard deviation of 6.7 days).⁴ This reduction is be considered clinically and economically significant. Allowing for a ~5% withdrawal rate we will recruit 150 patients per group (300 in total).

Recruitment numbers

300 participants will be recruited and randomised 1:1 intervention to routine clinical care, i.e. 150per group

9. Safety

The risks of stool samples, rectal swabs, vomitus samples and additional blood tests being taken are minimal and where occurring are likely to be of very low impact.

An Adverse Event (AE) is any untoward medical occurrence – there does not need to be a causal relationship between the occurrence and the study.

A Serious Adverse Event (SAE) is any adverse event that

- Results in death
- Is life threatening
- Requires hospitalisation or prolongation of existing hospitalisation
- Results in persistent or significant disability or incapacity
- Consists of a congenital anomaly or birth defect

As participants in ED are not yet hospitalised but have a reasonable likelihood of being admitted to hospital, patients enrolled in ED who are subsequently admitted to the hospital will not automatically be counted as having experienced a SAE.

Participants who are already admitted to AMU/ASU are already hospitalised however, an adverse event leading to prolongation of their existing hospitalisation would count as a SAE.

In the event of a SAE, the PI will be involved in deciding whether this was a study-related event.

SAEs occurring more than 30 days after the patient has left hospital will not be recorded or reported as SAEs because of the time lapsed in relation to the event and an acute infection or POC testing.

10. Statistical Evaluation

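### The stool or swab is collected after open-label allocation, so missing samples could differ by arm and bias the 11 secondary outcomes that depend on pathogen status or diagnostic yield

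*Protocol*

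**What the plan says.** **Eligibility (section 6).** One exclusion is that the patient "Declines to give stool sample and/or rectal swab". No time point is attached. An inclusion criterion requires that the patient "is able and willing to adhere to the study procedures".

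**Order of events (section 5).** Consent is agreed "in-line with the inclusion and exclusion criteria". Allocation follows: "Once a patient has been screened and consented a study team member will log onto the password-protected electronic randomisation website". The trial is open label.

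**Sampling (section 5).** Collection is described separately for each arm, under headings for patients already randomised. In the intervention arm research staff take a stool sample, with a rectal swab if stool cannot be produced in time, and the result is available in about an hour. For the other arm: "A stool sample and/or rectal swab will also be taken from patients in the control group and stored for testing at a later date". The timing is given as "Samples will be taken on enrolment, frozen and stored, and run on the FilmArray at least 30 days after collection". The control result has no bearing on that patient's care; its stated purpose is a direct comparison of diagnostic yield between the groups.

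**Outcomes and analysis (sections 5, 8 and 10).** The primary outcome is time in a side room. Outcome data are collected from electronic and physical case notes. Section 10 states an intention-to-treat analysis.

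**The concern.** Agreeing at consent to give a sample is not the same as giving one. The swab is sought only when stool is not forthcoming, and that becomes clear when sampling is attempted. As section 5 is laid out, the arm is known by then. Patients with vomiting alone are eligible, so some may have no stool to offer.

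The two arms also face different incentives. An intervention patient's swab leads to a prompt result for the clinical team. A control patient's swab is frozen and read at least 30 days later. Refusal or non-provision could therefore be more common among controls. The documents do not show that it is.

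What is at stake is any outcome that needs to know which organism, if any, a patient carried. If the patients with a known status are selected differently in the two arms, comparisons within the pathogen-positive and pathogen-negative groups, and the comparison of yield itself, are no longer protected by randomisation. Keeping everyone in the intention-to-treat set does not restore a sample that was never taken.

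**Working it through.** The protocol gives no figure for sample refusal, so there is none to reproduce. The check sets the sections side by side and then asks what size of effect could be derived.

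**1. Timing.** Section 5 gives the sequence screen, consent, randomise. Sampling appears only below that, under each arm. The exclusion in section 6 is worded as an act, declining, and is undated. Nothing says how a patient who consents, is randomised and then gives no sample is classified.

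**2. Outcomes that need a sample.** From the list in section 8:
- side-room duration in pathogen-positive and in pathogen-negative patients: 2
- proportion isolated, by pathogen status: 2
- proportion de-isolated, by pathogen status: 2
- time to de-isolation in pathogen-negative patients: 1
- antibiotic treatment with and without bacterial gastroenteritis: 2
- proportion with any pathogen and with a bacterial pathogen detected: 2

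Total: 2 + 2 + 2 + 1 + 2 + 2 = 11. This assumes that status is taken from the study sample, which fits the stated purpose of storing control samples.

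**3. The primary outcome.** It comes from case notes and needs no sample. If unsampled controls are kept, the shift in the control mean is zero. If they were removed, contrary to section 10, the shift would be (3 − f·m)/(1 − f) − 3. Here 3 days is the planning mean in section 8, f is the fraction of controls removed and m is their mean side-room days (both assumed):
- f = 5%, m = 0: 3/0.95 − 3 = +0.158 days
- f = 5%, m = 3: (3 − 0.15)/0.95 − 3 = 0
- f = 5%, m = 6: (3 − 0.30)/0.95 − 3 = −0.158 days
- over the same range of m, f = 2% gives ±0.061 and f = 10% gives ±0.333 days

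The sign depends wholly on m, which the documents do not give.

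**4. Diagnostic yield, as an illustration.** Let p be the true yield in an arm, u the unsampled fraction and q the yield those patients would have had. The observed yield among sampled patients is (p − u·q)/(1 − u), so the shift is u(p − q)/(1 − u). Take p = 0.54, the FilmArray detection rate that section 3 quotes from a pan-European study in a mixed population, as a placeholder. Let q run from 0 to 1:
- u = 2%: 0.02 × 0.54/0.98 = +1.1 points; 0.02 × (−0.46)/0.98 = −0.9 points
- u = 5%: 0.05 × 0.54/0.95 = +2.8 points; 0.05 × (−0.46)/0.95 = −2.4 points
- u = 10%: 0.10 × 0.54/0.90 = +6.0 points; 0.10 × (−0.46)/0.90 = −5.1 points

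These are outer limits for one arm under assumed u and p. Again both signs are possible.

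**5. The withdrawal allowance.** 141/0.95 = 148.4, rounded up to 149, so 150 per group fits the roughly 5% allowance in section 8. The protocol does not link that rate to sample refusal or to one arm, so it does not supply u.

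**The case against.** The strongest reply is that the exclusion is a screening criterion. It stands among the eligibility criteria, consent follows those criteria, and willingness to follow the study procedures is required before allocation. On that reading a patient who later refuses is non-adherent or withdrawn, not ineligible. This is the ordinary reading and it stands. It does not remove the gap between agreeing and providing.

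A reader might go further and infer that the criterion removes patients from the trial after allocation, mostly controls with short isolation, and so inflates the control mean in the primary comparison. The documents do not support this. Removal after allocation is nowhere stated, and it would contradict the intention-to-treat analysis in section 10. More refusals among controls is plausible but undocumented. Unsampled patients could have longer stays just as well as shorter ones. Sections 8 and 10 do, in places, describe the intervention group as those who received the test, which is a reason to state retention plainly but not evidence of removal.

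Two further replies have some force. Sampling on enrolment could be meant to precede allocation; if so, only the layout of section 5 needs correcting. The handling of missing samples may also be set out in a statistical analysis plan that is not shown. That is fair for the analysis, but the order of sampling and randomisation is fixed in the protocol, and an analysis rule cannot recover an uncollected sample.

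Finally, a literal reading of the and/or wording would exclude someone who offers stool but declines an unneeded swab. The protocol uses that phrase for the study specimen generally, so this is a point of clarity only.

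**Conclusion.** The point holds for the secondary outcomes. Collection is laid out after open allocation, the refusal criterion is undated, and controls gain nothing for their care from the sample. Missing samples could therefore differ by arm and bias the 11 outcomes counted above, even with every patient kept in the intention-to-treat set.

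The primary outcome is protected provided section 10 is followed, and no figure for bias in it should be quoted.

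The size and direction of any bias in the secondary outcomes cannot be derived from the documents. The yield ranges above show only what assumed fractions of missing samples could do. The conclusion rests on two assumptions: that pathogen status comes from the study sample, and that some consented patients will not provide one. It is a cheap improvement to the design, not a flaw that invalidates the main comparison.

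**What to change.** 1. Reorder section 5: consent, collect stool or swab, randomise, then run the sample (intervention) or freeze it (control). The later stool that section 5 requires after an initial swab test can stay where it is.
2. In section 6, state that the exclusion is judged at that collection step, before randomisation, and means declining both a stool sample and a rectal swab.
3. In section 10, state that any patient randomised without a sample stays in the intention-to-treat analysis of the primary outcome.

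The cost is one amendment and no extra procedure, because both arms are sampled at enrolment in any case. The test is not delayed, since it cannot start without the sample. The downside is that allocation waits for the sample, and a few consenting patients who then refuse sampling are never randomised. Section 8 reports that 100 of the 300 patients had already been recruited, so the new order can apply only to those not yet randomised. For patients already randomised, the number without a sample should be reported by arm.

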A stool sample from a patient with acute diarrhoea presenting to hospital in England would conventionally undergo a range of laboratory testing methods for different pathogenic organisms. The key methods include microscopy, culture, enzyme immunoassay and PCR.⁹ These methods vary in their turnaround times but culture takes several days to generate a result to clinicians. These slow turnaround times mean that patients presenting with suspected gastroenteritis are isolated and often treated with antibiotics empirically leading to unnecessary isolation facility use in those without infection and antibiotic usage in those without bacterial aetiology.

In addition, conventional diagnostic testing is not comprehensive and is insensitive for many pathogens leading to many missed diagnoses and lack of confidence in a negative result.

Potential benefits of molecular point-of-care testing in acute gastroenteritis

Improved pathogen detection compared to conventional testing

A pan-European observational study showed the pathogen detection rate in stool samples from patients with gastroenteritis could be improved from 18% using traditional methods, to 54% using the multiplex rapid PCR FilmArray Gastroenteritis Panel. Site selection bias, a mix of adult and paediatric and inpatient and outpatient populations and heterogeneous local testing methods weaken the findings. Nevertheless, this multicentre, cross-sectional study clearly shows a wide spectrum of pathogens were detected; 20 different GI pathogens were detected, out of 22 tested for, in around 700 stool samples.¹⁰

Other studies have suggested similar improvements in diagnostic yield, including a USbased study of 230 prospectively collected stool samples, with 8.3% positivity with conventional diagnostics compared to 33.3% positivity with the FilmArray GI panel. Again, a broad range of pathogens were observed.¹¹

A paediatric-based study comparing the aetiologic yield of standard-of-care microbiologic testing ordered by physicians with that of the multiplex FilmArray GI panel, showed that identification of a pathogen increased from 46% to 65%.¹² This suggests a syndrome-based approach to testing may be clinically beneficial.

Decreased length of hospitalisation

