The company product information sheet states "The FilmArray Gastrointestinal (GI) Panel tests for common gastrointestinal pathogens including viruses, bacteria and parasites that cause infectious diarrhea. *(sic)* The integrated FilmArray system brings sample to results in about an hour, with only 2 minutes of hands-on time."

The peer-reviewed published evidence relating to the diagnostic accuracy of the FilmArray Gastrointestinal Panel is discussed in the 'Background' section.

8. Analysis

The retrospective review of medical records will allow comparison of participants who received the rapid diagnostic test and controls managed with standard clinical care.

Primary outcome measure

• Duration of time in a side room

Secondary and exploratory outcomes

- Duration of time in a side room for pathogen positive patients
- Duration of time in a side room for pathogen negative patients

- Proportion of patients isolated in a side room
- Proportion of pathogen positive patients isolated in a side room
- Proportion of pathogen negative patients isolated in a side room
- Proportion of pathogen negative patients de-isolated
- Proportion of pathogen positive patient de-isolated
- Time to patient isolation in a side room
- Time to de-isolation in pathogen negative patients
- Proportion of patients treated with antibiotics
- Proportion of patients with bacterial gastroenteritis treated with antibiotics
- Proportion of patients without bacterial gastroenteritis treated with antibiotics
- Time to treatment with antibiotics
- Duration of antibiotics
- Duration of hospitalisation
- Proportion of patients with a pathogen detected
- Proportion of patients with bacterial pathogen detected
- Time to diagnosis
- Missed diagnoses
- Other medication use, complications (including acute kidney injury), ICU admissions, 30 day mortality, representation and readmission.
- Concordance between results obtained from rectal swab and stool culture
- Time from sampling to availability of results (Turnaround time)
- Patient satisfaction scores (using the modified NHS Adult Inpatient Survey Questionnaire 2016)

Sample size and power calculation

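### The swab concordance outcome names stool culture as comparator, which does not match the paired stool test that Section 5 describes

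*Protocol*

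**What the plan says.** Protocol Section 8, under secondary and exploratory outcomes, gives the outcome as "Concordance between results obtained from rectal swab and stool culture". It says nothing more about it.

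The procedure that would produce paired results is in Section 5, for the intervention arm. The study sample, whether stool or swab, is "analysed on the FilmArray using the Gastrointestinal Panel". If the swab was tested first, "a stool sample will be subsequently obtained at the earliest opportunity and then tested and the results checked to ensure concordance". Culture is not mentioned there. On routine testing the same section says: "Further laboratory stool testing will be at the discretion of the responsible clinical team". Stored control-arm samples are also to be run on the FilmArray, at least 30 days after collection.

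Section 3 (Conventional testing) treats culture as one method among several: "The key methods include microscopy, culture, enzyme immunoassay and PCR". Section 7 says the panel "uses nested RT-PCR followed by melt curve analysis to detect 22 targets". Section 15 names quantitative PCR as the reference assay for viruses and for some bacteria and parasites. It allows the study laboratory to culture stool where PCR is unsuitable, but does not require it.

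**The concern.** A concordance outcome for two sample types is interpretable when the assay is held fixed and only the sample changes. Section 5 appears to do that. Section 8 pairs a multiplex PCR result on a swab with a culture result on stool, so a disagreement could come from the sample, the assay or both, and the data could not separate them.

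The protocol itself expects the assays to differ. Section 3 calls conventional testing insensitive for many pathogens and cites a study in which detection was 18% by traditional methods and 54% by the FilmArray. A swab that reproduced the stool FilmArray result every time would still look discordant with culture.

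It matters because swab results are used during care: Section 5 has positive and negative results passed on in real time to infection control and to those allocating side rooms. Agreement between swab and stool is therefore worth reporting properly. As written, the listed outcome has no guaranteed data, and the planned paired test has no outcome that matches it.

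**Working it through.** The protocol gives no figure for this outcome to reproduce, so the check compares the sections, counts targets and illustrates the effect.

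**1. Comparator, section by section**

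- Section 8: swab result against stool culture.
- Section 5: swab result against a later stool sample that is tested; assay not named. FilmArray is the only assay described there for study samples.
- Section 3: culture is listed apart from PCR.
- No section defines stool culture as a term for the FilmArray result on stool.

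**2. Is a culture result assured?** No. Section 5 leaves further laboratory testing to the clinical team, and Section 15 permits study culture without requiring it. A participant tested first by swab may have no culture result.

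**3. Targets outside the reach of bacterial culture (Section 7)**

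- Viruses: 5, namely "Adenovirus F 40/41 Astrovirus Norovirus GI/GII Rotavirus A Sapovirus (I, II, IV and V".
- Parasites: 4, namely "Cryptosporidium Cyclospora cayetanensis Entamoeba histolytica Giardia lamblia".
- Bacteria: 13 (Campylobacter, C. difficile, Plesiomonas, Salmonella, Yersinia, Vibrio, V. cholerae, EAEC, EPEC, ETEC, STEC, E. coli O157, Shigella/EIEC).
- Total: 13 + 4 + 5 = 22, which matches the stated number.
- Viral or parasitic: (5 + 4)/22 = 9/22 = 41%.

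**4. One case.** A participant has norovirus on the swab FilmArray and on the stool FilmArray, and a negative bacterial culture. Under Section 5, read as FilmArray on both samples, the pair is concordant. Under Section 8 read literally, it is discordant although the two samples agree.

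**5. Ceiling on overall agreement (illustration only).** Let p be the proportion of swabs that are positive and s the share of positives with viral or parasitic targets only. Suppose swab and stool agree perfectly and culture finds every bacterial target. Agreement with culture then cannot exceed 1 − p × s.

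The protocol gives no p or s for this trial. For p, take two FilmArray positivity figures cited in Section 3, 54% and 33.3%. For s, take 0.41 (the share of targets, a placeholder and not a frequency) and 0.69. The latter uses the primary-care frequencies in Section 3: viruses 12 + 8.8 + 7.3 + 3.4 + 2.5 = 34.0; parasites 1.4 + 1 = 2.4; bacteria 13 + 2.4 + 1 = 16.4; so 36.4/52.8 = 0.69.

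- p = 0.54: 1 − 0.54 × 0.41 = 0.78; 1 − 0.54 × 0.69 = 0.63.
- p = 0.333: 1 − 0.333 × 0.41 = 0.86; 1 − 0.333 × 0.69 = 0.77.

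Under these assumptions the ceiling lies between 63% and 86%. Comparing FilmArray with FilmArray has no such built-in ceiling.

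**The case against.** The strongest reply is that stool culture is loose wording for stool sample. The procedure in Section 5 is clear enough to work from, and the outcome line does not change what is collected. No concordance analysis is defined, so nothing says that a viral detection will be scored as discordant with culture. That is fair as to likely intent. It does not remove the mismatch, because the outcome as worded defines a different comparator and an analyst could apply it.

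A comparison with culture might also be deliberate: Section 4 sets the FilmArray against standard laboratory methods, and Section 15 allows study culture. But Section 4 concerns ease of use and turnaround, and no section plans systematic culture in participants tested by swab.

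Several stronger readings are tempting and not supported:

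- **That 69% of detections could never agree with culture.** The percentages behind it sum to 52.8, while the same paragraph of Section 3 says at least half of cases have no pathogen, so the categories overlap or do not add. They are primary-care figures and omit C. difficile, a bacterial target on the panel. The figure serves only as an assumed upper value for s above.
- **That culture happens only when clinicians ask for it.** Section 15 leaves room for study culture.
- **That Section 5 expressly puts the later stool on the FilmArray.** It says only that the sample is tested; the assay is a strong inference.
- **That the outcome exists to show that a swab can replace stool, or that the trial would come to doubt its own swab results.** The protocol does not state that purpose, and the Section 5 check goes ahead whatever Section 8 says.

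The number of participants tested first by swab is not given, so the affected group may be small.

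**Conclusion.** The point holds as a mismatch between an outcome definition and the procedure meant to supply its data. Section 8 names stool culture; Section 5 plans a tested stool sample, most probably on the FilmArray. Taken literally, the outcome confounds assay with sample type, leaves 9 of 22 targets (41%) unconfirmable by bacterial culture, and depends on results that need not exist.

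The target count and the mismatch rest on the protocol's own text, together with the fact that bacterial culture does not detect viruses or parasites. That the later stool goes on the FilmArray is inferred. The 63% to 86% ceiling is illustrative and should not be quoted as an expected result.

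The scope is one secondary or exploratory outcome. The primary outcome, sample size, randomisation and comparison between arms are untouched. It is still worth correcting, because the stated comparator would make this outcome uninterpretable.

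**What to change.** In Section 8, reword the outcome as: concordance between the FilmArray result on the rectal swab and the FilmArray result on the same participant's subsequent stool sample. In Section 5, name the FilmArray as the assay for that later stool, once the investigators confirm that this is the intention.

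If a comparison with culture is also wanted, list it as a separate outcome, restrict it to culturable bacterial targets, and say which participants will have a culture result. The choice of agreement statistics, including any breakdown by target, can be left to the statistical analysis plan.

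The cost is one reworded outcome and one clarified sentence. No new sampling is needed, since the paired stool test is already planned. Only the optional culture outcome would add work.
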